8.13 Safety Management of Serum Creatinine

Serum creatinine may increase, at least temporarily, with the initiation of MRA treatment, especially in patients with more advanced CKD, most likely reflecting hemodynamic alterations. Therefore, serum creatinine will be measured at baseline and closely monitored systematically throughout this Phase 2 study. Study drug will be discontinued permanently if serum creatinine increases $\geq 50\%$ from baseline during the study treatment period.

8.14 Monitoring and Management of Blood Pressure

Blood pressure will be closely monitored throughout this study. At Screening, patients must have uncontrolled hypertension, defined as resting trough-cuff seated SBP \geq 140 and \leq 179 mmHg based on the mean of at least 2 current consecutive blood pressure readings at Screening and the end of the run-in period in the clinic. Blood pressures are obtained according to the AHA recommendations for accurate blood pressure measurement. Patients should avoid smoking, caffeine, or exercise within 30 minutes before measurement; empty his or her bladder; then sit quietly in a comfortable chair with back support for at least 10 minutes before a measurement; and remain still during the measurement. The patient's limb should be supported to measure blood pressure and ensure that the blood pressure cuff is at heart level, using the correct cuff size. Do not take the measurement over clothes. Blood pressure measurements should be performed in the same arm throughout the study. Measurement will be taken with a validated, oscillometric upper arm blood pressure monitor.

In all cases, dose and frequency of concurrent antihypertensive medications are expected to be maintained without change for 30 days prior to randomization. In general, patients should not add or adjust dose and/or types of the antihypertensive medications they are receiving during the screening period and throughout the duration of the study (unless they develop symptomatic hypotension). The dose of diuretic may be adjusted based on developing or resolved edema, weight gain or loss, or pulmonary congestion. Antihypertensive therapy may be modified if necessary during the safety assessment, following withdrawal of the study drug to maintain blood pressure control.

Diagnoses of hypertensive emergency require discontinuance of the study drug, and immediate treatment per local treatment guidelines. The occurrence of hypertensive urgency or a transient severe elevation in blood pressure may or may not require removal of a patient from the study drug but should be recorded as an adverse event and reviewed with the study Medical Monitor. AHA/American College of Cardiology definitions, clinical definitions, and treatment algorithms for hypertensive emergency, hypertensive urgency, or marked elevations in blood pressure appear in Appendix C.

Symptomatic hypotension or a confirmed trough-seated SBP < 90 mmHg based on the mean of at least 2 current consecutive protocol-required blood pressure readings, or otherwise obtained blood pressure reading) after the first dose of study drug at Day 1, should be reported as an adverse event of special interest. Investigators should evaluate and correct any potential reasons that may contribute to hypotension, such as dehydration, decreased blood volume, potential overdose of

antihypertensive medication (including study drugs), etc. If symptomatic hypotension or a confirmed trough-seated SBP < 90 mmHg occurs, Investigators may consider down-titration of antihypertensive medications (other than study drug) first. If symptomatic hypotension or a confirmed trough-seated SBP < 90 mmHg persists following down titration study drug should be permanently discontinued.

9 STATISTICS

9.1 Analysis Populations

The Intent-to-Treat (ITT) Population will consist of all randomized patients who take at least 1 dose of randomized study drug, have a baseline SBP measurement, and have at least 1 post-randomization SBP measurement. The ITT Population is the primary analysis population. All efficacy analyses will be performed for the ITT Population.

The Per-Protocol Population will include all ITT patients who have completed the 84-day double-blind treatment period without any major protocol deviations or violations. The Per-Protocol Population will be used to assess robustness of the primary analysis results. The major protocol deviations will be pre-specified prior to unblinding treatment codes for analyses.

The Safety Population will include all randomized patients who receive at least 1 dose of randomized study drug.

The PPK Population will include all randomized patients who receive at least 1 dose of randomized study drug and have at least 1 measurable concentration of total KBP-5074.

9.2 Statistical Methods

9.2.1 Demographic and Baseline Comparability

Patient disposition and analysis population data will be tabulated by treatment group with number and percentage of patients. Summary statistics will be provided by treatment group for demographics (eg, age, sex, race, and ethnicity) and for baseline efficacy variables (such as SBP, serum potassium, eGFR, creatinine, DBP, and UACR). For efficacy variables, baseline will be defined as the Day 1 (Visit 4) measurement. If the measurement at this visit is missing, then the last measurement prior to the first dose of randomized study drug will be used.

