4.2 Exclusion Criteria

Patients who meet any of the following criteria will be excluded from participation in the study:

- 1. Resting trough-cuff seated SBP ≥ 180 or < 140 mmHg, based on the mean of at least 2 current consecutive clinic blood pressure readings at Screening and the end of the placebo run-in period (Visit 3);
- 2. Serum potassium > 4.8 mmol/L;
- 3. Compliance with medications (including both open-label placebo and current antihypertensive medications) < 80% or > 120% during the run-in period (assessed at Visit 3);
- 4. Currently on an MRA (eg, spironolactone or eplerenone) other than KBP-5074, or received any MRAs during the last 3 months prior to Screening, or currently on any potassium supplements;
- 5. Chronic or intermittent use of a potassium binder for the treatment of hyperkalemia from 3 months prior to Screening until the end of study assessments, including but not limited to calcium polystyrene sulfonates (eg, sorbisterit, calcium resonium), sodium polystyrene sulfonates (eg, kayexalate, anti-kalium sodium), and patiromer (eg, Veltassa[™]) and sodium zirconium cyclosilicate (eg, Lokelma[™]);
- 6. Have routinely or chronically used or required potassium-sparing diuretics (eg, amiloride, triamterene) within 3 months prior to Screening until the end of study assessments;
- 7. History of known/suspected contraindications, allergy, or intolerance to MRAs (eg, spironolactone, eplerenone) or has a known hypersensitivity to KBP-5074, other MRAs, or related compounds;
- 8. Clinically significant hyperkalemia while on an angiotensin converting enzyme inhibitor, angiotensin receptor blocker, direct renin inhibitor, and/or MRA, requiring down-titration or discontinuation of above medication, or hospitalization for hyperkalemia within 3 months prior to Screening, or hyperkalemia > 5.6 mmol/L during the 2 weeks prior to Screening;
- 9. History/diagnosis of renal artery stenosis or history/diagnosis of renovascular hypertension;
- 10. Currently receiving HD, or peritoneal dialysis within 3 months prior to Screening, and those patients with an episode of acute kidney injury within 3 months of Screening;

- 11. History of a renal transplant, or impending renal transplant;

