6.2 Screening Visit (Visit 1)

The following procedures will be performed at Visit 1:

- Obtain informed consent:
- Assess eligibility criteria;
- Record demographics and medical history;
- Perform physical examination;
- Record height and weight;
- Calculate body mass index;
- Contact IRT;
- Perform 12-lead ECG in triplicate (patients should be resting in a supine position for at least 10 minutes prior to assessment);
- Obtain vital signs, including pulse rate, respiratory rate, and oral temperature;
- Obtain blood pressure;
 - Note: Patients must have uncontrolled hypertension, defined as resting trough-cuff seated SBP ≥ 140 and ≤ 179 mmHg, based on the mean of at least 2 current consecutive blood pressure readings in the clinic;
 - o Blood pressures are to be obtained according to the AHA recommendations for accurate blood pressure measurement. Patients should avoid smoking, caffeine, or exercise within 30 minutes before measurement; empty his or her bladder; then sit quietly in a comfortable chair with back support for at least 10 minutes before measurement and remain still during the measurement. The patient's limb should be supported to measure blood pressure to ensure that the blood pressure cuff is at heart level, using the correct cuff size. Do not take the measurement over clothes. Blood pressure measurements should be performed in the same arm throughout the study. Triplicate blood pressure measurements should be taken approximately 2 minutes apart with a validated, oscillometric upper arm blood pressure monitor. Trough cuff SBP and DBP values will be assessed based on the pre-defined blood pressure measurement guideline throughout the study. Pulse will be obtained simultaneously with blood pressure measurements;
- Obtain blood samples for:
 - o HIV, HbsAg, and HCV tests;
 - o Clinical laboratory tests (central laboratory; see Appendix B); and
 - o FSH (post-menopausal women only);

- Obtain urine sample for:
 - o Drug screen;
 - o Urinalysis (central laboratory; see Appendix B); and
 - O UACR:
- Obtain serum sample for potassium (local and central laboratories);
 - Note: Serum potassium should be $\leq 4.8 \text{ mmol/L}$ (local lab) to advance or continue to the placebo run-in Period;
- Obtain serum sample for creatinine (central laboratory);
- Obtain serum sample for pregnancy test (WOCBP only); and
- Record adverse events and concomitant medications.

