6.3.2 End of Open-Label Placebo Run-In Period (Visit 3)

The following procedures will be performed at Visit 3:

- Assess eligibility criteria;
- Check study drug accountability and collect unused study drug;
 - Note: If a patient's compliance to medications (including both open-label placebo and current antihypertensive medications) is < 80% or > 120%, he/she will not be eligible for the study and no further visits will be required;
- Record weight;
- Obtain vital signs, including pulse rate, respiratory rate, and oral temperature;
- Obtain blood pressure;
 - Note: Patients must have uncontrolled hypertension, defined as resting trough-cuff seated SBP ≥ 140 and ≤ 179 mmHg, based on the mean of at least 2 current consecutive blood pressure readings in the clinic;
 - o Blood pressures are to be obtained according to the AHA recommendations for accurate blood pressure measurement. Patients should avoid smoking, caffeine, or exercise within 30 minutes before measurement; empty his or her bladder; then sit quietly in a comfortable chair with back support for at least 10 minutes before measurement and remain still during the measurement. The patient's limb should be supported to measure blood pressure to ensure that the blood pressure cuff is at heart level, using the correct cuff size. Do not take the measurement over clothes. Blood pressure measurements should be performed in the same arm throughout the study. Triplicate blood pressure measurements should be taken approximately 2 minutes apart with a validated, oscillometric upper arm blood pressure monitor. Trough cuff SBP and DBP values will be assessed based on the pre-defined blood pressure measurement guideline throughout the study. Pulse will be obtained simultaneously with blood pressure measurements;
- Obtain urine sample for drug screen;
- Obtain serum sample for potassium (local and central laboratories);
 - O Note: Serum potassium should be $\leq 4.8 \text{ mmol/L}$ (local lab) to advance to randomization;
- Obtain serum sample for creatinine (central laboratory);
- Obtain blood sample for clinical chemistry (central laboratory; see Appendix B);
- Record adverse events and concomitant medications; and

• Instruct patient on 24-hour urine collection to be provided at Visit 4 and dispense laboratory materials for collection.

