6.4.2 Day 1 (Visit 4) \pm 2 Days

This visit is to be scheduled within 4 ± 2 days after the end of the run-in period (Visit 3).

The following procedures will be performed at Visit 4:

- Assess eligibility: Patients must have uncontrolled hypertension, defined as resting trough-cuff seated SBP ≥ 140 and ≤ 179 mmHg, based on the mean of at least 2 current consecutive blood pressure readings in the clinic. Prior to randomization, all patients are to have a serum potassium ≤ 4.8 mmol/L at both Screening and the end of the placebo run-in period; and a mean (Visit 1 and Visit 3) eGFR ≥ 15 and ≤ 44 mL/min/1.73 m².
- Record weight;
- Perform physical examination (pre-dose);
- Perform 12-lead ECG in triplicate (patients should be resting in a supine position for at least 10 minutes prior to assessment);
- Obtain vital signs, including pulse rate, respiratory rate, and oral temperature;
- Obtain blood pressure prior to study drug administration;
 - O Blood pressures are to be obtained according to the AHA recommendations for accurate blood pressure measurement. Patients should avoid smoking, caffeine, or exercise within 30 minutes before measurement; empty his or her bladder; then sit quietly in a comfortable chair with back support for at least 10 minutes before measurement and remain still during the measurement. The patient's limb should be supported to measure blood pressure to ensure that the blood pressure cuff is at heart level, using the correct cuff size. Do not take the measurement over clothes. Blood pressure measurements should be performed in the same arm throughout the study. Triplicate blood pressure measurements should be taken approximately 2 minutes apart with a validated, oscillometric upper arm blood pressure

monitor. Trough cuff SBP and DBP values will be assessed based on the pre-defined blood pressure measurement guideline throughout the study. Pulse will be obtained simultaneously with blood pressure measurements;

- Obtain blood sample for clinical laboratory tests (central laboratory; see Appendix B);
- Obtain urine sample for:
 - o Urinalysis (central laboratory; see Appendix B);
 - o Urine pregnancy test for WOCBP only (pre-dose);
 - o UACR; and
 - o 24-hour urine for UACR;
- Obtain serum sample for potassium (local and central laboratories);
- Obtain serum sample for creatinine (central laboratory);
- Obtain plasma sample for PK from all patients (prior to patient's release from the unit);
- Obtain serum sample for aldosterone;

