9.2.2 Analysis of Efficacy

9.2.2.1 Primary efficacy analysis

The primary efficacy analysis is to evaluate the change in trough-cuff seated SBP from baseline to Day 84 for the KBP-5074 doses compared to placebo. The endpoint for each patient is defined as the Day 84 cuff seated SBP measurement. If the measurement at this visit is missing or the patient discontinues early, the last post-baseline measurement during the double-blind period will be used.

The primary efficacy analysis will be carried out using a 2-way analysis of covariance (ANCOVA) model with treatment, baseline eGFR level (≥ 30 versus < 30 mL/min/1.73 m²), and background antihypertensive medication (2 or more) as factors, and the baseline SBP value as a covariate. The least-squares means, standard errors, and the 2-tailed 95% confidence intervals (CIs) for each treatment group and for the comparison will be estimated. The treatment difference between KBP-5074 doses and placebo will be estimated from the ANCOVA model. No multiple comparison adjustment will be used for this Phase 2 study.

The primary efficacy analysis will be based on the ITT Population. Other imputation methods for the primary efficacy endpoint will be explored. The supportive analysis will be carried out for the primary efficacy variable based on the Per-Protocol Population to examine the impact due to premature dropouts and/or major protocol deviations or violations.

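### Screening and Visit 3 SBP, already collected before randomisation, could enter the primary ANCOVA as a second SBP covariate for a modest gain in precision

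*Combined protocol and SAP*

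**What the plan says.** Section 9.2.1 fixes the baseline for efficacy variables at one visit: "baseline will be defined as the Day 1 (Visit 4) measurement". If that value is missing, "the last measurement prior to the first dose of randomized study drug will be used", which will normally be Visit 3.

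The primary model in Section 9.2.2.1 contains treatment, baseline eGFR level (two levels), and "background antihypertensive medication (2 or more) as factors, and the baseline SBP value as a covariate". Day 1 SBP is therefore the only SBP term, but not the only adjustment.

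Other SBP readings exist before randomisation. At Screening (Section 6.2), "Triplicate blood pressure measurements should be taken approximately 2 minutes apart with a validated, oscillometric upper arm blood pressure monitor". The same procedure is written into Section 6.3.2 for Visit 3, and into Section 6.4.2 for Day 1 itself, so the Day 1 baseline is one visit but three readings. The SBP entry limits in Sections 4.1 and 4.2 are applied "based on the mean of at least 2 current consecutive clinic blood pressure readings at Screening and the end of the placebo run-in period", so an eligible patient cannot lack either value. Section 9 gives these earlier readings no role as covariates.

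**The concern.** Three readings about 2 minutes apart average out the error within a visit. They do not remove the variation from one visit to the next. Day 1 SBP is thus a noisy measure of a patient's usual pressure, and readings from other visits can still help to predict Day 84 SBP once Day 1 is known.

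What is at stake is the precision of the two dose-versus-placebo contrasts. Section 9.2.7 sizes the trial so that the interval around an observed 5 mmHg difference excludes 0, and states no power. In a trial sized this way, a narrower interval obtained from data already in hand is worth having. Both covariates precede randomisation, so the treatment contrast being estimated does not change.

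**Working it through.** **1. The plan's own figure.** Inputs from Section 9.2.7: difference 5 mmHg, SD of change 15 mmHg, 95% interval, 10% to 15% dropout.

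n = 2 × (1.96 × 15 / 5)² = 69.1, so 70 per group; 70 × 1.15 = 80.5, so 81. Table 2 gives 81 and the text uses 80. Rounding n up and multiplying by 1.15 returns all nine cells of Table 2. The SD is that of the unadjusted change, so the sample size takes no credit for any covariate.

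**2. Simple bound, ignoring the entry limits.** Assume the same correlation r between any two visits. The share of Day 84 variance left unexplained is

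- Day 1 only: 1 − r²
- Day 1 plus the mean of Screening and Visit 3: 1 − 3r²/(1 + 2r)

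At r = 0.5 these are 0.750 and 0.625, a cut of 16.7%. Scaling so that the SD of change is 15, with half-width = 1.96 × residual SD × √(2/80):

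| r (assumed) | Residual SD | Half-width, mmHg | Variance cut |
|---|---|---|---|
| 0.3 | 12.1 → 11.6 | 3.75 → 3.58 | 8.7% |
| 0.5 | 13.0 → 11.9 | 4.03 → 3.67 | 16.7% |
| 0.7 | 13.8 → 12.1 | 4.29 → 3.74 | 24% |

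These cuts are too generous, because patients are selected to lie between 140 and 179 mmHg, which restricts the range of the covariates.

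**3. Simulation with the 140 to 179 limits at Screening, Visit 3 and Day 1.** Assumed: usual SBP mean 150, between-patient SD as shown, visit-to-visit SD 11, and noise added at Day 84 to bring the SD of change to about 15. There are 80 patients per group. Power is for a true 5 mmHg.

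| Between-patient SD | Residual SD | Half-width, mmHg | Variance cut | Power |
|---|---|---|---|---|
| 8 | 13.36 → 13.05 | 4.14 → 4.04 | 4.6% | 66% → 68% |
| 12 | 13.71 → 13.14 | 4.25 → 4.07 | 8.0% | 64% → 67% |
| 16 | 13.92 → 13.21 | 4.31 → 4.09 | 9.9% | 62% → 67% |

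Over a wider set of inputs, including partly serially correlated visit errors and the same limits at Visit 2, the cut is about 3% to 11% when the SD of change is about 14 to 16. Cuts of 16% or more appear only when it is about 11.

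**4. When the gain vanishes.** If correlation decays purely with time (first-order autoregressive), earlier visits add nothing once Day 1 is known, and the gain is 0. A stable patient component restores it: with a permanent share of 0.3 and a decaying share of 0.2, the cut without entry limits is 6.7%.

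**5. Cost.** With 240 patients and six model parameters (intercept, two for treatment, eGFR level, background medication as two levels, Day 1 SBP), 234 degrees of freedom remain. A useless extra covariate inflates variance by about 233/232 = 1.004, or 0.4%.

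**The case against.** Nothing in the plan is wrong here. ANCOVA on a pre-specified baseline, with a stated fallback, is standard; there is no bias, contradiction or missing rule. That stands in full.

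The gain also rests on inputs that the documents do not supply. Appendix A allows Screening up to 42 days before Day 1, so some decay in correlation is plausible, and the entry limits shrink the benefit. This also stands, and is why the range reaches down to about 3%, and to zero in the limiting case. Pure decay would, however, mean that patients have no stable usual SBP, which is unlikely when background therapy must be unchanged for 30 days before randomisation.

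A reader might infer more urgency from Section 9.2.7. With SD 15, 1.96 × 15 × √(2/n) gives half-widths of 4.65 mmHg at 80 per group, 4.90 at 72 (10% dropout) and 5.04 at 68 (15% dropout), so the interval seems barely to exclude 0 at 5 mmHg. The documents do not support that reading: 15 is the SD of unadjusted change, and the planned ANCOVA already adjusts for Day 1 SBP. Its half-width at 80 per group is about 3.8 to 4.8 mmHg in the scenarios examined with an SD of change of about 14 to 16.

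Visit 2 readings (Section 6.3.1) could be averaged in as well. Leaving them out is a choice made for simplicity.

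**Conclusion.** The point holds as an efficiency improvement. Day 1 SBP is the only SBP term in the primary model, and two further pre-randomisation SBP values exist for every eligible patient and go unused.

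At an SD of change near the planned 15 mmHg, the expected gain is about 3% to 11% of residual variance, or about 0.1 to 0.2 mmHg off the half-width. In patients, 80/0.97 = 82.5 and 80/0.89 = 89.9, so it is worth roughly 2 to 10 more per group. This assumes a stable patient component in SBP; the between-visit correlation is not in the documents.

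Two stronger inferences fail. The model does not adjust for Day 1 SBP alone, since eGFR level and background medication are also factors. Nor is the precision guaranteed or entirely free: the gain is conditional and a small cost is certain.

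**What to change.** In Section 9.2.2.1, before unblinding:

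- Keep Day 1 SBP as the baseline for the change score and as a covariate.
- Add the mean of Screening and Visit 3 SBP as a second continuous covariate.
- State that if Day 1 is missing and Visit 3 becomes the baseline under Section 9.2.1, Screening SBP alone is the second covariate, so that Visit 3 is not entered twice.
- Do the same for DBP with the DBP readings in the secondary analysis (Section 9.2.2.2).

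This takes a few lines of text and one degree of freedom. It needs no new visits, data or patients, and the sample size can stay as it is.

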9.2.1.1 Study drug exposure, compliance, and concomitant therapies

Overall percent compliance to study drug dosage regimen, calculated as percent of doses taken relative to doses scheduled to be taken, will be summarized by treatment group. Extent of exposure in days will be evaluated and summarized from the first dose date to the last dose date of randomized study drug.

Concomitant medication/therapy verbatim terms will be coded using the latest version of the World Health Organization Drug Dictionary. The number and percentage of patients taking new concomitant medications after first dose date will be summarized by Anatomic Therapeutic Chemical classification and preferred term for each treatment group.

